Question: Which communication strategy used during the clinical encounter is more effective in reducing pain interference over time for patients with chronic pain who were taking opioids at baseline?

Dependent variable: Pain interference as measured by PROMIS Pain Interference Score (T-Score, Continuous)

Independent variable: Comparator received, CDS vs. PEAT (Dichotomous)

Potential Covariates: Age, gender, race, ethnicity, mental health comorbidities, chronic pain diagnosis, use of other pain medications (neuropathic pain medications, NSAIDS, antidepressants), benzodiazepine use, number of office visits during intervention period, baseline HRQOL, encounter month, physician years of practice, physician gender, employment, SES.

Moderator Analyses: We will use statistical interactions examining the moderating effects of patient age, race, ethnicity, mental health comorbidities, chronic pain diagnosis, physician years of practice and physician gender on the relationship between comparator and pain interference.

Mediation Analyses: We will test whether confidence in decision and satisfaction with communication as measured by COMRADE Scores mediates the relationship between the comparator used and the pain interference outcomes.

Primary Outcome: Model 2: Hierarchical Linear Model (Longitudinal Analysis)

Question: Which communication strategy used during the clinical encounter is more effective in improving how satisfied patients feel over time after communicating with their physician about chronic pain treatment risks and benefits?

Dependent variable: CG-CAHPS

Independent variable: Comparator received, CDS vs. PEAT (Dichotomous)

Potential Covariates: Age, gender, race, ethnicity, educational level, mental health comorbidities, chronic pain diagnosis, use of other prescribed pain medications (neuropathic pain medications, NSAIDS, antidepressants) benzodiazepine use, number of office visits during intervention period, baseline HRQOL, encounter month, physician years of practice, physician gender, employment, SES.

Subgroup Analyses: We will use statistical interactions examining the moderating effects of patient age, race, ethnicity, education level, mental health comorbidities, chronic pain diagnosis; and physician years of practice and gender on the relationship between comparator and pain interference.

Secondary Outcome: Model 3: Hierarchical Linear Model

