Question: Which communication strategy used during the clinical encounter is more effective in improving patient's Health Related Quality of Life over time?

Dependent variable: PROMIS Physical Function, PROMIS Depression, and PROMIS Pain Interference Scores (T-Scored, Continuous)

Independent variable: Comparator received, CDS vs. PEAT (Dichotomous). **Potential Covariates:** Same as Model 2.

Secondary Outcome: Model 4: Hierarchical Generalized Linear Model

Question: Which communication strategy used during the clinical encounter is more effective in reducing opioid prescriptions of more than 90 Morphine Milligram Equivalents (MME) over time?

Dependent variable: Opioid Prescription over 90MME (Dichotomous)

Independent variable: Comparator received, CDS vs. PEAT (Dichotomous). **Potential Covariates:** Same as Model 2.

Other Analyses: We will also perform a differences-in-differences analysis at the beginning and the end of the intervention to determine which strategy resulted in greater reduction in high-risk prescriptions.

Secondary Outcome: Model 5: Hierarchical Generalized Linear Model

Question: Which communication strategy used during the clinical encounter is more effective in reducing co-prescriptions of opioids and benzodiazepines over time?

Dependent variable: Opioids and Benzodiazepines Co-Prescribed (Dichotomous)

Independent variable: Comparator received, CDS vs. PEAT (Dichotomous). **Potential Covariates:** Same as Model 2.

Other Analyses: We will also perform a differences-in-differences analysis at the beginning and the end of the intervention to determine which strategy resulted in greater reduction in high-risk prescriptions.

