E7. Data Source Adequacy (IR-1). We plan to collect several types of data for this study. For the PROs, we will collect data directly from patients through web-based questionnaires. We will collect some data on comorbidities and medication use through data collected for clinical care and billing purposes through the EHR. Given that this data is not collected for research purposes, errors, particularly with regards to ICD-10 codes, are possible. We will work with our data warehouse to ensure that the data are cleaned prior to analysis and our statistical analysis team, led by [name], who has experience with clinical data collection and analysis,¹⁴¹ will also conduct extensive exploratory data analysis to identify potential errors in the data.

E7. Missing Data

a. Methods to Prevent and Monitor Missing Data. We anticipate two sources of missing data: the failure of patients to complete the initial set of questionnaires and the loss of patients to follow-up. Monitoring of missing questionnaire data will occur in real-time as online questionnaires are completed, completed partially, or never started. For enrolled patients who do not respond to the questionnaires after baseline, we will conduct two follow-up phone calls to attempt to collect data. After the intervention study period has ended, we will attempt one last follow-up phone call with a sub-sample of non-respondents to see if they are similar to respondents (MD-1). If so, for the hierarchical linear model, maximum likelihood estimation will be consistent as long as the data are missing at random (MD-3).¹³⁷ We are aware of the potential between failure to complete survey elements, failure to use the educational tools, and reduced HRQOL. These hypothesized patterns will receive close scrutiny in the analysis of the mechanisms.

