b. Statistical Methods to Handle Missing Data and Sensitivity Analyses. If the data is not missing at random, we will use multiple imputation techniques to impute missing data for respondents (MD-2). We plan on using the *mi impute mvn* command in Stata and will generate 20 datasets compatible with the regressions planned for the final analyses. To insure that the imputation has proceeded as expected, we will visually inspect parameters from successive iterations of the model to determine if they have reached a stationary distribution. We will conduct sensitivity analyses with the dataset that includes imputed data as well as with a dataset that does not include imputed data to determine the effect of the multiple imputation and plan on reporting both results. These precautions will serve to identify autocorrelation in the imputed data and allow for proper maintenance of uncertainty in imputed values (MD-3).

c. Reporting Reasons for Dropout and Missing Data. We will drop data from patients who do not have any visits with their PCP during the intervention period or are lost to follow-up, but will compare descriptive statistics for these patients to patients with at least one visit to their PCP for sensitivity analysis (MD-4, MD-5).

E9. Project Milestones and Timeline.

During the first 3-6 months of the study project, we will train the project staff, refine the study protocol, develop the data dictionaries, and obtain IRB approval. We will hold monthly meetings with our patient partners to finalize the study design and discuss issues related to IRB approval. In Year 1, Q4, we will passively enroll eligible patients in the two study arms. In the 4 weeks before the intervention period, we will send baseline questionnaires via REDCap. In Year 2, we will begin the intervention. We will conduct weekly reports from our EHR data warehouse to determine enrolled patient visits. Enrolled patients will be sent CG-CAHPS survey one day after each primary care visit. Enrolled patients will also receive the PROMIS questionnaires once a month. We will perform monthly checks to assess the completeness of data to minimize missing data and will complete one set of interim data analyses in Year 2 to assess whether there are any issues with missing data. Full data analysis will

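### Under missing at random the plan relies on maximum likelihood alone, which does not recover a missing baseline HRQOL covariate; patients with outcomes but no baseline score would be deleted if it is adjusted for

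*Combined protocol and SAP*

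**What the plan says.** E7 (Missing Data), part a, expects missing data from "the failure of patients to complete the initial set of questionnaires and the loss of patients to follow-up". After the intervention period there will be "one last follow-up phone call with a sub-sample of non-respondents to see if they are similar to respondents". If they are similar, then for the hierarchical linear model "maximum likelihood estimation will be consistent as long as the data are missing at random". The text does not separate missing responses from missing covariates. The phone calls made during the study do not target a missed baseline: "For enrolled patients who do not respond to the questionnaires after baseline, we will conduct two follow-up phone calls".

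Part b states: "If the data is not missing at random, we will use multiple imputation techniques to impute missing data for respondents". It plans 20 imputed datasets compatible with the planned regressions, and results with and without imputation. Part c says that data from patients lost to follow-up, or without a PCP visit in the intervention period, are dropped.

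In E5.b, the potential covariates of Models 1 and 2 include "number of office visits during intervention period, baseline HRQOL, encounter month". Models 3, 4 and 5 take theirs by "Same as Model 2". E5.b describes growth models of change over time but does not say whether the baseline score is a response, a covariate or both.

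**The concern.** The first named source, a missed initial questionnaire, leaves the study's baseline HRQOL score missing. When that score is a covariate, the usual mixed-model likelihood conditions on it, and every row of a patient without it is dropped. The consistency property stated in part a concerns missing responses. It does not extend to this deletion, which is a complete-case analysis on a covariate.

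Imputation could fill the gap but is held back for the other branch. The allocation is also awkward, because standard multivariate-normal imputation, the method named in part b, itself assumes missing at random. It fits the branch that does not use it.

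At stake are patients who supplied outcome data, up to a year of monthly PROMIS scores, and the make-up of the analysed sample. In the milestone schedule, randomisation (B9, 7/30/2017) comes before the first baseline questionnaires (B12, 8/1/2017), so the loss is a post-randomisation exclusion. The same covariate list could carry it into Models 4 and 5, whose prescribing outcomes do not depend on questionnaires.

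**Working it through.** **1. Provisions side by side.**

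| Situation | Missing at random (part a) | Not missing at random (part b) |
|---|---|---|
| Follow-up response missing | Likelihood uses the patient's other responses | Imputation |
| Baseline HRQOL missing, used as covariate | Nothing stated; rows deleted | Imputation could fill it |
| Baseline HRQOL missing, used as month-0 response | Likelihood handles it | Likelihood or imputation |

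The gap is the middle cell of the first column.

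**2. Check of the mechanism.** Mixed models were fitted to simulated data: 80 PCPs with 12 patients each (960), six follow-up responses per patient, baseline deleted at random.

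| Baseline missing (assumed) | Patients with outcomes | Kept, baseline as covariate | Kept, baseline as response |
|---|---|---|---|
| 20% | 960 | 768 | 960 |
| 40% | 960 | 562 | 960 |

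**3. The plan's sample size.** E5.c gives ICC 0.02, α 0.05 (two-sided assumed), power 90% and a difference of 0.3 SD.

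- Without clustering: n = 2(1.96 + 1.2816)² / 0.3² = 233.5 per arm.
- E5.c states 320 per arm, so the design effect is 320 / 233.5 = 1.370.
- Cluster size is not stated. From 1 + (m − 1) × 0.02 = 1.370, m = 19.5, or 320 / 19.5 = 16.4 clusters per arm.
- Inflation: 640 × 1.5 = 960, or 480 per arm. This allows a loss of 1 − 640/960 = 33.3%.

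**4. Power after deletion.** The share f with outcomes but no baseline is not in the documents; 10% to 30% is assumed. With k clusters per arm held fixed and N the starting number per arm: n = N(1 − f), m = n/k, effective n = n / [1 + (m − 1) × 0.02], power = Φ(0.3 × √(effective n / 2) − 1.96).

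Example, N = 480, f = 10%, k = 16.4: n = 432, m = 26.4, design effect 1.507, effective n = 286.6, power = 94.9%.

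| f | N = 480, implied clusters | N = 480, 80 PCPs (40 per arm) | N = 320, implied clusters |
|---|---|---|---|
| 10% | 94.9% | 98.1% | about 88% |
| 20% | 93.2% | 97.0% | about 85% |
| 30% | 91.0% | 95.2% | about 81% |

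With the implied clusters, 480 per arm comes down to exactly 90% at one-third deletion, because 480 × 2/3 = 320. The last column applies only if other losses have already used the whole inflation. None of these figures counts any precision gained by adjusting for baseline.

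**The case against.** **The deletion is inferred, not stated.** Baseline HRQOL is only a potential covariate, and a growth model can take baseline as its month-0 response. Routine-care PROMIS scores (E6.d) might also supply some baseline values. This stands as a limit: the point is conditional on baseline being a covariate. But the plan lists it as one and does not say that routine-care scores will serve as baseline.

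**Part b could rescue these patients.** Its imputed datasets could include baseline covariates. So it would be wrong to infer that patients are lost whenever baseline HRQOL is in the model. The loss belongs to the missing-at-random branch.

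**The plan does not use likelihood for both sources.** A reader might infer that from part a, but part c drops patients lost to follow-up. Parts a and c do not agree on that group.

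**Power is protected.** A reader might subtract losses from 320 per arm and report power of 81%. E5.c inflates to 480 per arm, partly for loss to follow-up and non-response, so that figure holds only once the inflation is spent elsewhere. The objection stands, with one qualification: E5.c also assigns the inflation to model variables and subgroup analyses.

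**Bias is not shown.** One could assume deletion of 30% in one arm and 20% in the other, with deleted patients 2 T points worse, and get 0.3 × 2 − 0.2 × 2 = 0.2 points. The documents give neither the split nor the 2 points. If the model's covariates explain why deleted patients are worse, the adjusted contrast need not be biased. E9 describes no difference by arm in sending the baseline questionnaires. Part a does acknowledge a possible link between survey non-completion, non-use of the educational tools and reduced HRQOL, so the risk cannot be dismissed.

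**Other covariates.** Employment, SES and education are sometimes questionnaire items, but the available text does not show their source here. The point therefore rests on baseline HRQOL.

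**Conclusion.** The point holds in conditional form. Under missing at random, the plan names a missed initial questionnaire as a source of missing data and provides only a method that does not recover a missing covariate. If baseline HRQOL is adjusted for as a covariate, patients with outcomes but no baseline are deleted after randomisation from Models 1 to 3, and possibly from Models 4 and 5. Patients who never answer any questionnaire contribute nothing to the questionnaire outcomes either way, so for Models 1 to 3 the avoidable loss is confined to those with follow-up responses but no baseline.

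The sure costs are precision and a selected sample. Their size is unknown. At an assumed 10% to 30%, power from 480 per arm stays at about 95% to 91% with the implied clusters, and higher with 80 PCPs. It drops below the planned 90% only when other losses add to the deletion. Bias in the arm contrast is possible but not demonstrated. The calculation assumes a two-sided test, fixed cluster numbers and a cluster size inferred from E5.c.

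**What to change.** 1. State for each model whether the baseline score is a response or a covariate.
2. In Models 1 and 3, enter the pre-intervention score as the month-0 response of the growth model, using only scores taken before the intervention. Alternatively, impute baseline HRQOL under missing at random in the main analysis, with an imputation model that respects the clustering.
3. In the other models, impute baseline HRQOL and any other incomplete baseline covariate in the main analysis, not only when data are judged not missing at random.
4. Keep departures from missing at random for sensitivity analysis.
5. Reconcile part a with part c's dropping of patients lost to follow-up.

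The cost is SAP wording and model code; no new data are needed. The downside is an added assumption, either a common baseline mean in both arms or an imputation model. The common mean is less secure for patients enrolled after cluster randomisation, and the milestones run enrolment to 12/31/2018 (E2), well after the intervention starts on 1/1/2018 (C1). If that is a concern, allow separate arm means at month 0 or use the imputation option.

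### The missing-data method is chosen by a similarity check that does not bear on missing at random, and neither branch of the choice tests a departure from it

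*Combined protocol and SAP*

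**What the plan says.** E7 Missing Data, part a, sets out one final call, after the intervention period, "with a sub-sample of non-respondents to see if they are similar to respondents (MD-1). If so, for the hierarchical linear model". The second of these sentences, which opens with a condition on the result of the call, goes on to state that "maximum likelihood estimation will be consistent as long as the data are missing at random". Part b gives the other branch: "If the data is not missing at random, we will use multiple imputation techniques to impute missing data for respondents", using the Stata command mi impute mvn with 20 datasets. It adds: "We will conduct sensitivity analyses with the dataset that includes imputed data as well as with a dataset that does not include imputed data", with both results to be reported.

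Part a also recognises a possible link between "failure to complete survey elements, failure to use the educational tools, and reduced HRQOL" and says that these patterns will be examined closely. Part c drops patients who have no PCP visit or are lost to follow-up, and "will compare descriptive statistics for these patients to patients with at least one visit to their PCP for sensitivity analysis".

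The plan does not say which variables the call-back compares, what counts as similar, how many non-respondents are to be called or reached, how they are selected, or whether the comparison is made within arms.

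**The concern.** The choice of method for the outcome models turns on a comparison that answers a different question. Equal means in respondents and non-respondents bear on whether data are missing completely at random. MAR is a weaker and different condition: given what has been observed, missingness does not depend on the unseen values. Non-respondents can differ from respondents under MAR, and can look the same when MAR fails.

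The second branch does not repair this. Imputation from a multivariate normal model fitted to the observed data, with no shift or selection term described, rests on MAR too. It is invoked exactly when MAR is judged to fail.

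The arm matters because the primary result is a CDS versus PEAT contrast. Response bias that is equal in both arms largely cancels from that contrast, while bias that differs between arms does not. Under E4.c only PEAT patients are sent the educational tools, so the mechanism that part a itself names can operate differently by arm.

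**Working it through.** **Logic of the rule.** Two cases show that it sorts on the wrong property.

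- *Different, yet MAR.* Suppose patients with worse baseline pain interference answer less often, and response depends on nothing further. Non-respondents then have worse scores on average, so the check fails. Maximum likelihood with baseline in the model remains valid.
- *Similar, yet not MAR.* Suppose the non-respondent minus respondent gap is +0.3 SD in one arm and −0.3 SD in the other, unexplained by observed data, with equal numbers reached. The overall gap is (0.3 − 0.3)/2 = 0, while the between-arm difference in gap is 0.3 − (−0.3) = 0.6 SD. A comparison that ignored arm would pass.

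**Inputs.** E5.c gives an effect of 0.3 SD, α 0.05 and 640 patients (320 per arm), inflated by 50%: 640 × 1.5 = 960. That allows for 1 − 640/960 = 33% loss. E4.d expects about 30% of 4,000 eligible patients, or 1,200, to complete every questionnaire. The plan states no figure for the call-back itself, so there is none to reproduce.

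**Assumptions.** Similar is read as a non-significant two-sided 5% test. There are 640 respondents, SD is 1, scores are independent (clustering ignored), and the *n* non-respondents reached are split equally between arms.

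**Formulas.**

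- Overall gap: SE = √(1/640 + 1/n).
- Between-arm difference in gap: SE = √[2 × (1/320 + 2/n)].
- Chance of missing a true difference d: Φ(1.96 − d/SE) − Φ(−1.96 − d/SE).

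Example with n = 50. Overall: SE = √(0.00156 + 0.02) = 0.147, 0.3/0.147 = 2.04, miss 47%. Between arms: SE = √[2 × (0.003125 + 0.04)] = 0.294, 0.3/0.294 = 1.02, miss 82%.

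| Reached (n) | Overall gap 0.3 SD missed | Between-arm difference 0.3 SD missed | 95% CI half-width, between-arm difference |
|---|---|---|---|
| 20 | 74% | 90% | 0.89 SD |
| 50 | 47% | 82% | 0.58 SD |
| 100 | 20% | 71% | 0.42 SD |
| 200 | 4% | 54% | 0.32 SD |

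With 1,200 respondents instead of 640, the overall miss rates at 20, 50 and 100 reached are 74%, 45% and 18%, and the between-arm rate at 200 is 50%.

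**What an unseen difference could do.** In an unadjusted comparison of respondents, with the same non-response fraction f in both arms, bias in the arm contrast = f × between-arm difference in gap. For a difference of 0.3 SD this is 0.33 × 0.3 = 0.10 SD at 33% non-response. At 70% it is 0.70 × 0.3 = 0.21 SD. The 70% is an upper illustration: E4.d counts completion of all questionnaires, and partial responders still contribute data. A likelihood model that uses baseline and earlier scores would remove the part of the bias that those scores explain.

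**The case against.** The plan is more careful than a quick reading suggests. It keeps MAR as an explicit condition for maximum likelihood. It commits to showing imputed and non-imputed results together, which softens the effect of a data-driven choice. It promises scrutiny of the pattern it fears and a descriptive comparison of dropped patients. E9 adds an interim look at missing data, and E4.e extracts EHR variables on all auto-enrolled patients, which would allow further comparison. Model 1 in E5.b is longitudinal and lists baseline HRQOL as a potential covariate.

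All of this stands, and it rules out some stronger readings. A reader might infer that the call-back comparison is pooled over arms; the text does not mention arms, so the most that can be said is that a by-arm comparison is not specified. A reader might infer that the sub-sample is small; no size is given, and with 200 reached an overall 0.3 SD gap would be missed only about 4% of the time. A reader might also infer that the call-back is the only check, or that similarity alone is taken to validate the likelihood analysis. Neither is supported.

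What the objection does not answer is the logic. None of the other checks sets a decision rule. The two reported analyses share the MAR assumption, so agreement between them says nothing about a departure from it.

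**Conclusion.** The point holds as a fault in a stated rule, not merely as missing detail. Similarity cannot decide whether MAR holds, the not-MAR branch uses a method that assumes MAR, and no MNAR analysis is planned. The missing criterion and the unspecified by-arm comparison add to this.

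The miss rates are conditional: they rest on reading similar as a non-significant 5% test, on 640 independent respondents, and on call-back sizes that the plan does not give. Under those assumptions an overall gap as large as the target effect is likely to be seen once 100 to 200 are reached, whereas a between-arm difference of that size would still be missed about half the time at 200. These are detection rates, not estimates of bias. A reader might infer that the arm contrast will be biased; the documents do not show that, only that the plan could not tell.

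**What to change.** 1. Delete the conditional wording in part a and the switch to imputation in part b. Name the maximum likelihood hierarchical model as primary whatever the call-back shows. An imputed analysis may stay as a supplement, labelled as assuming MAR.
2. Draw the planned call-back sub-sample separately within each arm. Report the non-respondent minus respondent difference in PROMIS Pain Interference by arm, and the between-arm difference in that gap, each with a 95% CI. Note that those who answer a last call may differ from those still unreached.
3. Make no pass/fail claim from this comparison. A margin of 0.3 SD, for example, could not be met with fewer than about 233 reached even if the observed difference were exactly zero: setting 1.96 × √[2 × (1/320 + 2/n)] = 0.3 gives n ≈ 233.
4. Pre-specify an MNAR sensitivity analysis, either delta-adjusted by arm or pattern-mixture, with a range of deltas that covers the call-back estimates.

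The cost is SAP wording, a stratified draw for calls already planned, one table and a little more analysis. The downside is that the report will usually have to say that differential response bias is not excluded.
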